11.10.4.4. Operation Characteristics

Power and type I error rate are examined across scenarios for the distribution of assumed true ORRs for each cohort. The power is the probability of declaring efficacy within an individual cohort when the true underlying ORR is greater than its corresponding historical control. Type 1 error rate is the probability of declaring efficacy within an individual cohort when the true underlying response rate is equal to the historical control.

The power and type I error rate are dependent upon the sample sizes and response rates across the distribution of cohorts. When the treatment effects are the same across all cohorts (either all responsive or all non-responsive), estimation efficiencies, due to borrowing, result in very good operating characteristics, even in cohorts with low sample sizes. The type I error rate is controlled to ≤ 0.08 across all cohorts (All Null scenario). The design maintains power 90% to 97% for all four cohorts (All Great scenario). Also, the design exhibits reasonable power to detect a moderate level of activity (All moderate scenario).

When the treatment effects vary across cohorts, the amount of appropriate borrowing also varies, impacting the operating characteristics. However, under all scenarios, the design

maintains at least 80% power for the positive cohorts. The '2 null, 2 positive' and '3 null, 1 positive' cases investigate design performance where at least half of the cohorts are not responsive. In this situation, the type I error rate is inflated between 0.1 and 0.13 the power is at least 81% for the positive cohorts. Generally, improvement in the overall distribution of treatment effects tends to coincide with slight increases in type I error rate and moderate increases in power.

Overall type I error rate, the probability of claiming efficacy in at least one group under the null hypothesis is 0.23.

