Simulation studies were conducted to evaluate the performance of the Bayesian Hierarchical design under various assumptions for the distribution of true ORRs across the TNBC, mTCC, and NHL cohorts. Operating characteristics including power, type I error, estimation of the ORR, and the probability of halting enrollment at interim analyses were assessed.

When the treatment effects are similar across TNBC, mTCC, and NHL histologies, the design maintains power 88% to 97% and type I error rate ≤0.1. Estimation efficiencies due to borrowing result in very good operating characteristics in these situations, even in histologies with low sample sizes. Table 21 provides similar operating characteristics for scenarios where not all histologies align in terms of efficacy performance.

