11.10.4.2. Software Details

Simulations were conducted by the software provided by Berry Consultants. For each assumed scenario, 500 sets of trials were simulated. Posterior distributions were estimated via Markov chain Monte Carlo methods using 50,000 iterations for each analysis, discarding the first 2,000 iterations for each analysis as burn-in.

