11.10.4.3. Trial Sample Size and Simulation Scenarios

Sample size requirements for halting enrollment at interim analyses for simulations is based on the number of subjects enrolled; while in practice, they will be based on the number of subjects with available response data. This discrepancy is due to software feasibility but should not have a significant impact on operating characteristics of the design. Simulations assumed interim analyses occurred every 4 weeks, with the first interim analysis occurring once 40 subjects have been enrolled. The time from subject entry until the response assessment was performed is assumed to be 24 weeks. The maximum length of time for each study is 120 weeks ± 6 weeks (roughly 2.5 years).

Although actual enrollment may vary, predicted enrollment during a 2-year time period is incorporated into the simulations. Cohort, projected enrollment and the historical control and clinically meaningful response rates used in simulations are shown in Table 21.

	Cohorts						
	TNBC	mTCC	NHL[+]	NHL[-]			
Project Enrollment in	32	40	25	25			
2-year time period; n							
Max Sample size; n	32	40	25	25			
Scenarios							
All Null	10%	15%	10%	10%			
All Positive	25%	30%	30%	30%			
All Moderate	20%	20%	20%	20%			
2 Null, 2 Positive	25%	15%	30%	10%			
3 Null, 1 Positive	10%	15%	30%	10%			
Proportion of Trials that I	Proportion of Trials that Declare each Cohort Efficacious (Measure of Power or Type I Error						
Rate)							
All Null	0.05	0.10	0.06	0.05			
All Positive	0.92	0.88	0.95	0.96			
All Moderate	0.67	0.39	0.58	0.57			

Table 21Simulation Scenarios and Design Characteristics

		Coh	orts			
	TNBC	mTCC	NHL[+]	NHL[-]		
2 Null, 2 Positive	0.82	0.12	0.87	0.13		
3 Null, 1 Positive	0.09	0.10	0.81	0.11		
Proportion of Trials that I	Declares Early Fut	tility				
All Null	0.50	0.52	0.47	0.42		
All Positive	0.03	0.05	0.02	0.01		
All Moderate	0.09	0.22	0.06	0.08		
2 Null, 2 Positive	0.09	0.41	0.04	0.24		
3 Null, 1 Positive	0.39	0.45	0.06	0.31		
Proportion of Trials that Pick all the Positive Cohorts						
All Null	N/A					
All Positive	0.76					
All Moderate	N/A					
2 Null, 2 Positive	0.74					
3 Null, 1 Positive	0.81					

Due to the 'borrowing' nature of the model, the design is evaluated across a variety of scenarios for the distribution of true ORRs across the four cohorts. These are shown in Table 21.

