The "All Positive" scenario assumes all cohorts are responsive at the defined clinically meaningful RR levels. The "Null" case assumes all cohorts are nonresponsive at the historical control RRs. The "All Moderate" scenario assumes all cohorts show moderate RR levels in between the historical control and clinically meaningful RR levels. The other three scenarios consider various situations where cohorts are either responsive (at the clinically meaningful RR level) or not (at the historical control RR level).

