11.10.4.5. Stopping Early

Table 21 also presents the proportion of trials that halt enrollment early for futility across simulation scenarios. Since the study requires at least ten subjects in a particular cohort prior to stopping early for futility, the ability for a cohort to stop early is largely dependent upon the projected maximum sample size and enrollment rate per cohort. The overall distribution of treatment effects across cohorts also impacts the likelihood of halting enrollment early.

When the expected 2-year enrollment is greater than 20, non-responsive cohorts stop early for futility between 26% and 47% of the time. Across simulation scenarios, responsive cohorts generally do not stop early for futility.

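### The protocol's text gives operating characteristics for the hierarchical cohorts that its own Table 21 does not show, and the 2% GBM futility cut given as an example does not produce Table 18

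*Protocol*

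**What the plan says.** **Hierarchical cohorts (TNBC, mTCC, NHL[+], NHL[-]).** Three parts of the protocol describe how this design performs.

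- Section 11.10.4.4 limits the type I error to "0.08 across all cohorts (All Null scenario") and adds "The design maintains power 90% to 97% for all four cohorts (All Great scenario"). For scenarios that mix null and positive cohorts it says "In this situation, the type I error rate is inflated between 0.1 and 0.13".
- Section 11.10.4.5 says that, where projected two-year enrolment exceeds 20, "non-responsive cohorts stop early for futility between 26% and 47% of the time".
- Section 11.9.1 says that with similar effects across histologies "the design maintains power 88% to 97% and type I error rate" is at most 0.1.

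The figures themselves are in Table 21 (section 11.10.4.3), in the block headed "Proportion of Trials that Declare each Cohort Efficacious" and the futility block below it. Section 11.10.4.2 gives the simulation size: "For each assumed scenario, 500 sets of trials were simulated".

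**GBM.** Protocol 11.3, repeated in SAP 3.1.1, uses a Beta(0.03, 0.07) prior and rejects the null at 8 or more of 28 subjects progression-free at six months. It offers a predictive probability below 2% as an example of a futility cut and prints stopping counts for 10 to 27 evaluable subjects (protocol Table 18, SAP Table 4). It also allows a stop if fewer than 1 of the first 13 is progression-free. Section 11.9.1 states a type I error of 0.086 and 80% power.

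**The concern.** The prose in 11.10.4.4 and 11.10.4.5 describes Table 21 but does not match it. Two further signs suggest that it may describe a different simulation run. All Great is not a scenario name in Table 21. The text also says "The other three scenarios consider various situations where cohorts are either responsive" or not, although only two scenarios remain in the table once All Null, All Positive and All Moderate are set aside.

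These error rates belong to the final rule in section 4.3.3.2, under which a dose is declared efficacious in a cohort when the posterior probability reaches 0.87. For mTCC, 11.10.4.4 gives a more favourable type I error and power than Table 21 or 11.9.1.

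For GBM, a reader who applies the printed 2% example would derive stopping counts that differ from the printed ones. The 13-subject wording also differs from Table 18, which stops at 1 of 13.

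**Working it through.** **1. Text against Table 21.** Cohort order is TNBC, mTCC, NHL[+], NHL[-].

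| Quantity | Text | Table 21 |
|---|---|---|
| Type I error, All Null | at most 0.08 (11.10.4.4); at most 0.1 (11.9.1) | 0.05, **0.10**, 0.06, 0.05 |
| Power, All Positive | 90–97% (11.10.4.4); 88–97% (11.9.1) | 0.92, **0.88**, 0.95, 0.96 |
| Type I error, null cohorts in mixed scenarios | 0.1–0.13 | 0.12, 0.13 (2 null); **0.09**, 0.10, 0.11 (3 null) |
| Early futility, null cohorts | 26–47% | **0.50**, **0.52**, 0.47, 0.42 (All Null); 0.41, **0.24** (2 null); 0.39, 0.45, 0.31 (3 null) |

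Three of the nine null futility entries fall outside 26–47%. All four cohorts have projected two-year enrolment above 20 (32, 40, 25, 25), so the condition in 11.10.4.5 excludes none of them.

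**2. Simulation error.** With 500 trials the 95% interval is p ± 1.96·√(p(1−p)/500).

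- p = 0.10: standard error 0.0134, interval 0.074 to 0.126.
- p = 0.88: standard error 0.0145, interval 0.852 to 0.908.

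Both intervals include the figures in the text (0.08 and 0.90). The documents therefore show that text and table disagree, but not which mTCC rate is right.

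**3. GBM: reproducing the plan's figures.** The inputs are p0 = 0.17, p1 = 0.35, N = 28, success at 8 or more, and prior Beta(0.03, 0.07). An exact forward recursion on the Table 18 counts, removing the stopped paths at each n from 10 to 27, reproduces both printed probability columns to four decimals (for example 0.1552 and 0.0135 at n = 10, 0.1817 and 0.0199 at n = 13). It gives a type I error of 0.0859, against 0.086 stated, and power of 0.8056, against 80% stated.

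**4. GBM: which cut gives Table 18.** After x progression-free of n, the number progression-free among the remaining 28 − n is beta-binomial with parameters 0.03 + x and 0.07 + n − x. The predictive probability of success is P(at least 8 − x more among 28 − n).

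| x/n | Predictive probability | 2% rule | Table 18 |
|---|---|---|---|
| 1/12 | 1.33% | stop | continue |
| 2/16 | 1.68% | stop | continue |
| 3/20 | 1.15% | stop | continue |
| 5/25 | 1.20% | stop | continue |
| 1/13 | 0.75% | stop | stop |
| 4/23 | 0.90% | stop | stop |

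The largest value at any Table 18 stop is 0.90% (4/23), and the smallest at any continue is 1.15% (3/20). Cuts of 0.90%, 0.95%, 1.0%, 1.1% and 1.15% match all 18 rows. A cut of 0.85% fails at n = 17 and 23, 1.16% fails at n = 20, and 2% fails at n = 12, 16, 20 and 25.

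**5. GBM: size of the difference.**

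| Rule | Type I error | Power | Stopped by n = 13 under the null | Expected N under the null |
|---|---|---|---|---|
| Table 18 (cut about 1%) | 0.0859 | 80.6% | 33.7% | 19.5 |
| 2% cut | 0.0836 | 79.7% | 37.4% | 18.5 |

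**6. Check of the method.** The same calculation with the cuts stated for ER+BC (8%) and HPV+ (1%) matches every row of Tables 19 and 20. It gives 0.098 and 81.5% against the stated 0.10 and 82%, and 0.052 and 87.0% against 0.05 and 87%. GBM is the only one of the three whose printed cut and table disagree.

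**The case against.** The strongest reply is that little depends on this. Recruitment is closed and the mTCC gaps are within simulation error. Section 11.9.1 already gives the less favourable figures and points to Table 21. The posterior declaration is described as informing decisions that rest on the totality of the data, and the SAP's efficacy tables report observed response rates with exact intervals and list no posterior-probability display. All of that is right, and it limits the consequence. It does not reconcile text and table: simulation error explains why the true rate is uncertain, not why prose about a table differs from that table. Protocol 11.10.2.3 also still plans to report the posterior probability for each cohort.

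On GBM, the 2% is only an example, the stopping counts are called a guideline, and nowhere is 2% said to have generated Table 18. That is fair, but an example printed beside a table should be consistent with it. Stated power does not settle which cut was used, since 79.7% rounds to 80% and 80.6% to 81%; the table rows and the type I error do. The 13-subject sentence is permissive and does not forbid a stop at 1 of 13, which the 2% rule in the same paragraph would allow, so it is a wording slip. It also adds nothing as written, because 0 of 13 implies 0 of 10, where a stop is already allowed.

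Some side points are minor: 0.09 against 0.1 is one-decimal rounding, 97% is a loose upper bound rather than a contradiction, and the first simulated look at 40 enrolled is disclosed.

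**Conclusion.** The concern holds. As written, 11.10.4.4 and 11.10.4.5 misstate Table 21: for mTCC, type I error is 0.10 against at most 0.08 and power is 0.88 against at least 0.90; for null cohorts, early futility is 24–52% against 26–47%. This rests on reading text against table. The hierarchical simulation was not rerun, so the conclusion is that the protocol is inconsistent, not that error control fails.

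For GBM, the 2% example is not the cut behind Table 18 or the stated type I error of 0.086; a cut between about 0.90% and 1.15% is. This rests on the stated prior, N = 28 and success at 8 or more. Four stopping counts differ by one subject, with differences of about 0.002 in type I error, 0.8 points in power and one subject in expected null sample size.

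One related gap has an unquantified effect: the simulation takes its first look at 40 enrolled, whereas 4.3.3.2 also allows one once any cohort has 10 evaluable subjects.

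**What to change.** - Restate 11.10.4.4 and 11.10.4.5 from Table 21: type I error up to 0.10 under All Null and 0.09–0.13 for null cohorts in mixed scenarios, power 88–96% under All Positive, and early futility 24–52% for null cohorts. Change 97% to 96% in 11.9.1. Alternatively, rerun the simulation and align text and table to the new output.
- Use the Table 21 scenario names and correct the scenario count in 11.10.4.3.
- State that the simulated first look at 40 enrolled leaves out the trigger of 10 evaluable subjects in any cohort.
- In protocol 11.3 and SAP 3.1.1, reconcile the example cut and the 13-subject wording with the stopping table. A cut of about 1% and 1 or fewer of 13 are what agree with the printed table and the stated type I error.

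The cost is wording in two documents and, optionally, one simulation rerun. The hierarchical figures become slightly less favourable. No reported estimate changes.

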4.3.3.1. GBM Cohort

In Part 2, the GBM cohort will employ a Bayesian adaptive design that allows the study to be frequently monitored with the constraint of both Type I and Type II error rates. The first interim analysis will be conducted after a minimum of 10 evaluable subjects who have had at least three post-baseline assessments, have progressed or died, or have permanently discontinued from study treatment. Up to 28 subjects may be enrolled in the GBM cohort; for details of the design and decision rules, refer to Section 11.3.

4.3.3.2. mTCC, TNBC, and NHL Cohorts

For mTCC, TNBC and NHL cohorts, a "basket" Bayesian hierarchical modeling design that allows the trial to be frequently monitored with the constraint of both Type I and Type II error rates will be used. Clinical response will be defined as ORR, per standard evaluation criteria (see Section 14.4 for definitions of response assessments and criteria). Bayesian hierarchical modeling will be used to investigate the clinical activity of GSK3326595 in the four tumor-specific cohorts of subjects. Hierarchical modeling allows information about the treatment effect in one cohort to be 'borrowed' when estimating the treatment effect in another cohort [Berry, 2013].

Clinical activity will be monitored through frequent interim analyses. The first interim analysis will be conducted when about 40 evaluable subjects are enrolled across the four tumor-specific cohorts (mTCC, TNBC, p53 WT NHL, and p53 mutant NHL) at a dose level based on RP2D or at least 10 evaluable subjects are available in any cohort. Subjects treated at the RP2D in Part 1, with disease subtypes under study in Part 2, will be incorporated into clinical activity analysis provided that they are evaluable. Each subsequent interim analysis can be conducted after every five additional subjects become evaluable. The timing of subsequent interim analyses will be based on the enrollment rate into each of the cohorts with the expected duration of Part 2 of the trial to be 104 weeks. A subject is evaluable for the interim futility analysis if they have either progressed or died, withdrawn from the study treatment, or are ongoing and have completed at least two post baseline disease assessments.

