Decisions are based on whether the posterior probability that the ORR exceeds its corresponding historical control is sufficiently low compared to fixed statistical thresholds. If this posterior probability is sufficiently low within a given cohort (≤ 0.15), then enrollment may be halted early for futility. At the final analysis and after the study has been closed, if the posterior probability is sufficiently high (≥ 0.87), then the dose will be declared efficacious for that cohort. Separate from model estimates, the observed ORR will also be reported for each cohort.

Enrollment into each disease-specific cohort will continue during the conduct of each interim analysis subsequent to the decision of whether or not to declare futility. The total number may be increased up to a total of 32 evaluable subjects for the TNBC cohort, up to a total of 25 evaluable subjects for each of the two NHL cohorts, and up to 40 evaluable subjects for the mTCC cohort, depending on the results observed; a separate decision will be made for each disease cohort. Enrollment into each tumor specific cohorts can only be terminated for futility (i.e., lack of clinical activity), notwithstanding the provisions of Section 5.5; otherwise enrollment will continue to the planned maximum sample size in each cohort. Inference stemming from the Bayesian hierarchical model of GSK3326595 efficacy in subjects harboring these four tumor types are intended to inform decision making. Actual decisions will depend on the totality of the data.

Subjects enrolled in Part 1 may be included in the Part 2 efficacy analysis provided that they were treated at the RP2D and have a disease under study in Part 2.

The decision to terminate a disease-specific cohort will not depend solely on the results of the statistical model but will take all factors into account, including the results of the model, safety, tolerability, PK, and PD data. In some cases (e.g., under-representation of a given predictive biomarker in the subjects treated at the time of interim analysis), additional subjects in a cohort may be enrolled even if the model suggests a low likelihood of activity in that tumor type.

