11. STATISTICAL CONSIDERATIONS AND DATA ANALYSES

11.1. Hypotheses

In Part 1, the primary endpoints of this study are safety and tolerability; the MTD and RP2D will also be determined. No formal statistical hypotheses will be tested. The primary focus will be on determining the recommended dose for further exploration, the safety profile, and the PK of GSK3326595 in subjects with advanced solid malignancies. Analyses will be descriptive and exploratory.

The primary goal of Part 2 is to evaluate disease-specific clinical activity in subjects with select solid tumors and NHL. The cohorts will be terminated for futility based on interim analysis described in Section 11.9.6.

- For TNBC and ER+BC, efficacy is defined as a clinically meaningful response rate (defined as the percentage of subjects that have achieved a CR or PR) of 25% relative to a 10% historical control response rate.
- For mTCC, efficacy is defined as a clinically meaningful response rate (defined as the percentage of subjects that have achieved a CR or PR) of 30% relative to a 15% historical control response rate.
- For recurrent GBM, efficacy is defined as a clinically meaningful improvement in the rate of subjects who remain progression-free at six months (defined as a 35% six-month PFS rate relative to a 17% historical six-month PFS rate).
- For ACC and HPV-positive solid tumors, efficacy is defined as a clinically meaningful response rate (defined as the percentage of subjects that have achieved a CR or PR) of 30% relative to a 10% historical control response rate.
- For NHL (both p53 wild-type and p53 mutant cohorts), efficacy is defined as a clinically meaningful response rate (defined as the percentage of subjects that have achieved a CR or PR) of 30% relative to a 10% historical control response rate.
- For NSCLC, efficacy is defined as a clinically meaningful response rate (defined as the percentage of subjects that have achieved a CR or PR) of 30% relative to a 10% historical control response rate. An interim futility analysis will be used to determine the scope of further development in this cohort.

The primary goal of Part 3 is to evaluate the safety and tolerability of GSK3326595 in combination with pembrolizumab in solid tumors. No formal statistical hypotheses will be tested.

11.2. mTPI Method

The mTPI design [Ji, 2010] is an extension of the toxicity probability interval method [Ji, 2007] and employs a simple beta-binomial hierarchic model. Decision rules are based on

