11.9.6. Interim Futility Analysis

Interim data will be evaluated to monitor efficacy and safety. For the GBM cohort, a planned interim analysis for futility will be performed when at least 10 evaluable subjects have been enrolled in this expansion cohort. Enrollment may be stopped early for toxicity or lack of efficacy, should various criteria occur based on accrued data. The design criterion for early stop for futility based on Bayesian Predictive Adaptive Design is described in Section 11.3. For TNBC, mTCC, and NHL cohorts, the decision criteria for early stop for futility based on Bayesian Hierarchical model are described below. The decision will be made for each individual disease-specific cohort. For the ACC capsule cohort, one interim futility analysis will be performed when first treated 10 subjects become evaluable. If there are 1 or fewer responders in these 10 subjects, the cohort will be stopped early for futility. For the ACC tablet cohort, one interim futility analysis will be performed when the first 17 treated subjects become evaluable. If there are 2 or fewer responders in these 17 subjects, the cohort will be stopped early for futility. This rule is intended as a guideline, development decisions will depend on the totality of the data. For ER+BC cohort, the first interim analysis will be conducted when at least 10 subjects become evaluable. The details about interim decision rules are specified in Section 11.6. For HPV+ cohort, the first interim analysis will be conducted when at least 10 subjects become evaluable. The details about interim decision rules are specified in Section 11.7.
For the NSCLC cohort, one interim futility analysis will be performed when first treated 10 p53 wild-type subjects become evaluable. If there are 1 or fewer responders in these 10 subjects, the cohort will be stopped early for futility.

For TNBC, mTCC, and NHL cohorts, the therapeutic effect will be declared insufficient, and termination of enrollment will be recommended, if a minimum of 10 subjects become evaluable and the posterior probability that the confirmed ORR is greater than its corresponding historical control (C_j) is sufficiently low (<15%) based on the hierarchical model. That is,

P ($\pi_j > C_j$ | current data) < 15%, for the j-th cohort, j=1,..4

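### The basket-design simulations never show one inactive cohort among three active ones; under the protocol's own model its type I error is about 0.20 for NHL and TNBC, against at most 0.13 in the scenarios shown

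*Protocol*

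**What the plan says.** Protocol Section 4.3.3.2 introduces the basket design as one "that allows the trial to be frequently monitored with the constraint of both Type I and Type II error rates". If a cohort's posterior probability of beating its historical control reaches 0.87 at the final analysis, "then the dose will be declared efficacious for that cohort". Interim futility applies when that probability is "sufficiently low (<15%) based on the hierarchical model" (Section 11.9.6).

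Section 11.9.1 gives a type I error of at most 0.1 when effects are similar across histologies, then refers to Table 21 for similar operating characteristics when they are not. Section 11.10.4.3 says that "the design is evaluated across a variety of scenarios for the distribution of true ORRs across the four cohorts". Table 21 lists five: All Null; All Positive; All Moderate; 2 Null, 2 Positive; and 3 Null, 1 Positive. After describing the first three, the text continues: "The other three scenarios consider various situations where cohorts are either responsive (at the clinically meaningful RR level) or not". The table holds only two of that kind.

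For those two, Section 11.10.4.4 reports that "the type I error rate is inflated between 0.1 and 0.13 the power is at least 81% for the positive cohorts". It adds that a better overall distribution of effects tends to bring a slight rise in type I error.

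**The concern.** Borrowing pulls an inactive cohort's estimate towards its active neighbours. Among patterns built from the protocol's own null and target rates, the pull is strongest when the other three cohorts are all active, and that pattern is missing. The highest null-cohort rate a reader can find is 0.13, and nothing warns that the untested pattern goes well beyond it. At stake is how to read a declared success. If three cohorts respond, a success in the fourth may rest on the other three rather than on its own data, more often than any published figure suggests.

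**Working it through.** **Inputs.**
- Null and target ORR (Section 11.1): TNBC "25% relative to a 10% historical control response rate"; mTCC "30% relative to a 15% historical control response rate"; each NHL cohort 30% against 10%.
- Maximum n (Table 21): 32, 40, 25 and 25.
- Model (Appendix 11): Dirichlet process with α = 2; within a cluster θ_j ~ N(μ, τ²), μ ~ N(0, 1.82), τ² ~ IG(3, 0.5).
- Simulation settings (Section 11.10.4.3): looks every 4 weeks from the 40th enrolment, 24-week response delay, 120-week cap. Futility below 0.15 with at least 10 subjects; success at 0.87 or more.

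**Assumptions where the text is silent.** η_j is taken as the historical control C_j. Accrual is Poisson, reaching each maximum over two years. There is no efficacy claim after a futility stop. The printed 1.82 could be a variance or an SD, so both were run (variance 1.82, or 1.82² = 3.31). If it is 1.8² with a lost superscript, the variance is 3.24, close to the SD reading.

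**Method.** θ_j = logit(π_j) − logit(C_j). The four cohorts have 15 partitions, each with prior weight 2^k × Π(n_c − 1)!, where k is the number of clusters and n_c their sizes. Each cluster's likelihood is integrated numerically over μ and τ². Success means P(θ_j > 0 | data) ≥ 0.87.

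**Step 1: reproduce Table 21** (proportion declared efficacious, TNBC / mTCC / NHL[+] / NHL[-]).

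| Scenario | Table 21 | 1.82 as variance | 1.82 as SD |
|---|---|---|---|
| All Null | 0.05 / 0.10 / 0.06 / 0.05 | 0.069 / 0.078 / 0.066 / 0.064 | 0.069 / 0.070 / 0.061 / 0.066 |
| All Positive | 0.92 / 0.88 / 0.95 / 0.96 | 0.916 / 0.882 / 0.946 / 0.951 | 0.908 / 0.872 / 0.953 / 0.952 |
| 2 Null, 2 Positive | 0.82 / 0.12 / 0.87 / 0.13 | 0.824 / 0.130 / 0.891 / 0.123 | 0.809 / 0.131 / 0.882 / 0.137 |
| 3 Null, 1 Positive | 0.09 / 0.10 / 0.81 / 0.11 | 0.094 / 0.111 / 0.840 / 0.095 | 0.099 / 0.106 / 0.821 / 0.099 |

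Table 21 rests on 500 trials per scenario (Section 11.10.4.2), so an entry of 0.13 carries ±1.96 × √(0.13 × 0.87/500) = ±0.029. The mixed rows agree within that kind of error. The least good match is mTCC under All Null, slightly below the stated 0.10.

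**Step 2: the missing scenario.** Type I error of the single inactive cohort, the other three at target:

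| Inactive cohort | 1.82 as variance | 1.82 as SD | No interims (variance) |
|---|---|---|---|
| TNBC | 0.194 | 0.193 | 0.199 |
| mTCC | 0.160 | 0.177 | 0.167 |
| NHL[+] | 0.201 | 0.212 | not run |
| NHL[-] | 0.204 | 0.209 | 0.206 |

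These use 10,000 trials (variance) or 5,000 (SD); the Monte Carlo SE at 0.20 is √(0.2 × 0.8/5,000) = 0.006 or less. Other codings, varying accrual and interim handling, widen the ranges to 0.19-0.22 for NHL, 0.18-0.22 for TNBC and 0.13-0.22 for mTCC. The recomputed All Null futility rates (0.31-0.48) are mostly below Table 21's 0.42-0.52. That matters little here: removing the interims altogether moves the result by less than 0.01.

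**Step 3: why it happens.** Take NHL[-] at full size with 4 responders of 25. Analysed alone, its posterior is about 0.77, which fails. With 8/32, 12/40 and 7/25 in the other cohorts, the same 4/25 gives about 0.90, which succeeds. Alone, 5 responders are needed, and P(X ≥ 5 | n = 25, 10%) = 0.098. With that support 4 suffice, and P(X ≥ 4 | n = 25, 10%) = 0.236. Because the cut moves with the other cohorts' results, the overall rate falls between the two, at about 0.20.

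**The case against.** Several points on the other side stand. A reader might infer that 0.10-0.13 is wrong. It is not: the protocol ties it to the two mixed scenarios shown, and it reproduces. A reader might also infer that a numerical limit has been broken. None is set for mixed scenarios: the limit of 0.1 in Section 11.9.1 is for similar effects, and Section 11.10.4.4 openly reports inflation and an overall rate of 0.23 under the null. Nor does the count of three scenarios show that a run was dropped. Other text there does not match Table 21 either (an All Great scenario, and an All Null bound of 0.08 against a tabulated 0.10), so a stale count is as likely.

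It is tempting to say that the design was never tested with one NHL cohort active and the other not. It was: both mixed rows have NHL[+] at 30% and NHL[-] at 10%. What is new is TNBC and mTCC being active as well.

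Safeguards also exist. Observed ORRs and independent estimates are promised (Protocol Sections 4.3.3.2 and 11.4; SAP Section 3.1.2), and decisions are not to rest on the model alone. Recruitment has stopped, so a new simulation cannot change the design. But SAP Section 3.1.2 still bases final evaluations on this model, and Protocol Section 11.10.2.3 has the posterior probability reported for each cohort, so its error rate still matters for interpretation. An observed rate with its interval does not show whether the 0.87 threshold would have been met without borrowing.

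**Conclusion.** The point holds as an omitted scenario with a material consequence. The largest null-cohort type I error reported is 0.13. With one inactive cohort among three active ones, the protocol's own model gives about 0.20 for NHL and TNBC, at least double the 0.05-0.10 tabulated under All Null. A flat one in five for any inactive cohort would overstate it: mTCC is less certain, and the bottom of its range (0.13) is no higher than the figure already shown. The result assumes that the active cohorts sit at their target rates. With NHL[-] inactive and the other three at only 20-25%, it was 0.164. For NHL and TNBC, the reading of 1.82 and the handling of interims do not bring it below 0.18. The statements that type I error is constrained, that operating characteristics are similar when histologies differ, and that the rise is slight are not supported for this case.

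**What to change.** Run 1 Null, 3 Positive with each of the four cohorts inactive in turn and add the rows to Table 21. Correct the count of mixed scenarios in Section 11.10.4.3. Restate per-cohort type I error as ranging from 0.05-0.10 under All Null up to about 0.20, remove the description of the rise as slight, and reword Sections 4.3.3.2 and 11.9.1 to match. State whether 1.82 is a variance or an SD, and define η_j. Wherever a hierarchical posterior is reported against 0.87, show that cohort's no-borrowing posterior beside it, in addition to the independent estimates already planned. The cost is one simulation run, one extra column in the report and a less favourable stated figure.
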